6.4. Analysis Visit Window

Data analyzed by-visit-analysis (including efficacy, laboratory data, visit sign, ECG) will be summarized by the study scheduled visits described in the study protocol and SAP, “Schedule of Event”. The analysis visit windows will be exhaustive so that all available values obtained from unscheduled visits, early termination (ET) visit and end of treatment (EOT)/end of study (EOS) have the potential to be summarized. No analysis visit window mapping will be applied for the PK and ADA data.

Under protocol amendment 6, the planned study duration was up to three years or until dupilumab became commercially available in the geographic region of the patient. Protocol amendment 7 was adopted in order to permit those patients in France, Germany Poland and Japan who had already completed three years of treatment to either continue or re-start treatment through 31 December 2017. Patients who were in the safety follow-up period were permitted to resume treatment. Patients who had an End of Study visit were permitted to re-enter the study after being re-consented. Patients who had completed 3 years of treatment resumed treatment in a newly created series of visits called the “treatment extension” period. All patients were scheduled to have an End of Treatment visit on or around 31 December 2017.

Protocol amendment 8 extended the treatment period for up to 5 years for patients in Poland and Finland and to September 2018 in France. Again, patients who had previously had an End of Treatment visit under Amendment 7 and were in the safety follow-up period were permitted to resume treatment. Patients who had an End of Study visit were permitted to re-enter the study after being re-consented.

As a consequence of these two amendments, certain patients from these countries experienced gaps in treatment. One gap occurred between the Amendment 6 EoT date and resumption of treatment under Amendment 7. In addition, patients from Poland experienced a second treatment gap from the EoT date under Amendment 7 and resumption of treatment under Amendment 8.

The data collected at the scheduled visits under protocol amendment 7 and protocol amendment 8 for patients from these countries was collected outside of previously defined visit windows. Hence the analysis visit window will be done separately for data collected under protocol amendment 7/8 for patients from France, Germany, Poland, Japan and Finland and all remaining data. **All remaining data** consists of:

- data collected up to protocol amendment 6 for patients from France, Germany, Poland, Japan and Finland
- data from all other countries

Analysis visit window mapping for all remaining data

No analysis visit windows will be applied for the study scheduled visits except unscheduled visits, early termination visit, the end of treatment/ end of study visits, which are V30 (week 148), V25 (week 112) and V25 (week 108) for patients from UK, V31 (week 164) and V31 (week 160) for all countries except UK.

The following analysis visit windows will be used to map the unscheduled visits, early termination, end of treatment/ end of study visits, based on the study day:

Visit	Target Day	Analysis Visit Window Based on Study day*
Screening	<1	<1
Baseline	1	1
Week 1	8	[2,11]
Week 2	15	[12,18]
Week 3	22	[19, 25]
Week 4	29	[26, 43]
Week 8	57	[44, 71]
Week 12	85	[72, 99]
Week 16	113	[100, 127]
Week 20	141	[128, 155]
Week 24	169	[156, 183]
Week 28	197	[184, 211]
Week 32	225	[212, 239]
Week 36	253	[240, 267]
Week 40	281	[268, 295]
Week 44	309	[296, 323]
Week 48	337	[324, 351]
Week 52	365	[352, 393]

Visit	Target Day	Analysis Visit Window Based on Study day*
Week 60	421	[394, 449]
Week 68	477	[450, 505]
Week 76	533	[506, 561]
Week 84	589	[562, 617]
Week 92	645	[618, 673]
Week 100	701	[674, 729]
Week 108	757	[730, 785]
Week 116	813	[786, 841]
Week 124	869	[842, 897]
Week 132	925	[898, 953]
Week 140	981	[954, 1009]
Week 148	1037	[1010, 1093]
End of study	1149	>=1094
	785 for UK	>=730

*study day is calculated relative to the date of first study drug injection.

Analysis visit window mapping for data collected under protocol amendment 7/8 for patients from France, Germany, Poland, Japan and Finland

Analysis visit windows will be applied to map all study scheduled visits except extension end of study visit or end of study visit under protocol amendment 7 or 8, based on the study day. Data collected at extension end of study visit or end of study visit under protocol amendment 7 or 8 will be summarized using the nominal visit (i.e. extension end of study visit or end of study visit).

Visit	Target Day	Analysis Visit Window Based on Study day*
Screening	<1	<1
Baseline	1	1
Week 1	8	[2,11]
Week 2	15	[12,18]
Week 3	22	[19, 25]
Week 4	29	[26, 43]
Week 8	57	[44, 71]
Week 12	85	[72, 99]
Week 16	113	[100, 127]
Week 20	141	[128, 155]

Visit	Target Day	Analysis Visit Window Based on Study day*
Week 24	169	[156, 183]
Week 28	197	[184, 211]
Week 32	225	[212, 239]
Week 36	253	[240, 267]
Week 40	281	[268, 295]
Week 44	309	[296, 323]
Week 48	337	[324, 351]
Week 52	365	[352, 393]
Week 60	421	[394, 449]
Week 68	477	[450, 505]
Week 76	533	[506, 561]
Week 84	589	[562, 617]
Week 92	645	[618, 673]
Week 100	701	[674, 729]
Week 108	757	[730, 785]
Week 116	813	[786, 841]
Week 124	869	[842, 897]
Week 132	925	[898, 953]
Week 140	981	[954, 1009]
Week 148	1037	[1010, 1065]
Week 156	1093	[1066, 1149]
Week 172	1205	[1150, 1261]
Week 188	1317	[1262, 1373]
Week 204	1429	[1374, 1485]
Week 220	1541	[1486, 1597]
Week 236	1653	[1598, 1709]
Week 252	1765	[1710, 1793]
End of study	1821	>=1794

*study day is calculated relative to the date of first study drug injection.

In general, the following order will be used to select the record for analysis at given visit:

1. Scheduled visit
2. Early termination (ET) or end of study (EOS), whichever comes first if scheduled visit not available
3. Unscheduled visit if both scheduled visit and ETV/EOT/EOS are not available

For the multiple measurements of the same test in the same window, the following rules will be used to pick up the analysis value:

- If multiple valid values of a variable within an analysis visit window, the closest from the target study day will be selected.
- If the difference is a tie, the value after the targeted study day will be used.
- If multiple available values of a variable exist within a same day, then the first value of the day will be selected.

Analysis visit window mapping for weekly pruritus NRS

For the weekly pruritus NRS collected via IVRS, the following analysis visit windows will be used based on the study day:

Visit	Target Day	Analysis Visit Window Based on Study day*
Screening	<1	<1
Baseline	1	1
Week 1	8	[2,11]
Week 2	15	[12,18]
Week 3	22	[19, 25]
Week 4	29	[26, 32]
Week 5	36	[33, 39]
Week 6 onwards (every week)	43 (every 7 days)

* study day is calculated relative to the date of first study drug injection.

If there are multiple patient reported NRSs in the same week, then the average value of all scores in the week will be used for analysis.

Analysis visit window mapping for Ophthalmological Examination

No analysis visit windows will be applied for the ophthalmological exam scheduled visits in the sub-study. Data will be summarized using the nominal visit.

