2.3. Study Plan (Schedule of Study Assessment)

The study consists of a screening period, a treatment period and a follow-up period. The dose level, the duration of treatment period and follow-up period were modified for the study through several protocol amendments. These modifications are outlined in [Table 1](#).

Table 2: Study dose level and study duration under each protocol version

Protocol Version	Country	Dose Level (mg)	Duration of Treatment Period	Duration of Follow-up period
Original and amendment 1	Global	200	100 weeks	16 weeks
Amendment 2 and 3	Global	300	100 weeks	16 weeks
Amendment 4	Global	300	148 weeks or until commercially available	16 weeks
Amendment 5 and 6	Great Britain	300	100 weeks	16 weeks
Amendment 6	Global, Hungary, Japan	300	148 weeks or until commercially available	16 weeks
Amendment 7	Global, Hungary	300	148 weeks or until commercially available	12 weeks
Amendment 7*	France, Germany, Poland, Japan	300	Extend treatment period through approximately 31 December 2017	12 weeks
Amendment 7	Great Britain	300	100 weeks	12 weeks
Amendment 8**	Poland, Finland	300	Extend treatment period to up to 5 years (week 260)	12 weeks
Amendment 8**	France	300	Extend treatment period to approximately September 2018	12 weeks

* Note: Under protocol amendment 7 for France, Germany, Poland and Japan, patients who had already completed the End of Treatment visit under protocol amendment 6 were permitted to resume treatment with study drug. Patients who had completed the End of Study visit were permitted to re-enter the study. The treatment period ended for all patients in these countries on or about 31 December 2017.

** Note: Patients in Poland, Finland and France who had completed their End of Treatment/End of Study visit as per amendment 7 were permitted to resume treatment/re-enter the study provided that no more than 12 weeks had elapsed since their End of Study visit. The duration of the overall treatment period for patients in Poland and Finland was extended to 5 years, and to September 2018 for patients in France.

The study flow diagrams under protocol amendment 7 and 8 are provided in [Figure 2](#), [Figure 3](#), [Figure 34](#) and [Figure 35](#) below:

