5.7. Analyses of Efficacy Variables

The efficacy variables will be summarized for all patients in SAF. The continuous efficacy variables will be summarized using number of patients, means, SD, minimums, medians, Q1, Q3 and maximums. Categorical efficacy variables will be summarized using patient counts and proportion. No formal statistical hypothesis testing will be performed. The graph of mean value for continuous variable or proportion for categorical variable by visit will be provided.

All observed values, regardless of whether rescue treatment is used or data is collected after withdrawal from study treatment will be used for analysis. No missing values will be imputed.

For the categorical efficacy variables, the proportion of patients with each response at each visit will be calculated using the number of patients with a non-missing value at the visit as the denominator.

As described in Section 5.6, there are up to two potential “treatment gaps” due to patient re-entry to the study for protocol amendments 7 and 8 for patients from Germany, France, Poland and Japan. The primary focus of the efficacy data will be on the data collected prior to these potential “treatment gaps”.

- If the “treatment gap” is ≤ 8 weeks, then all efficacy data will be summarized together, i.e. data will be analyzed as if the patient had been dosed continuously
- If the “treatment gap” is > 8 weeks, efficacy data collected before and after the treatment gap will be summarized separately.

Data collected under end of study visit (i.e. off-treatment measurement at the end of 12-week or 16-week safety follow up period) will be summarized separately from the data while the patient was on treatment.

For the analysis of Pruritus NRS, the weekly NRS collected during the safety follow-up period, during the treatment gap between amendments 6 and 7, and between amendments 7 and 8 will be separated from the NRS collected during treatment. The primary focus of NRS data will be on the data collected during treatment.

Subgroup analyses for efficacy

Different subgroups within the overall SAF population will be defined as below. The analyses will be performed for the secondary efficacy variables related to EASI, IGA and pruritus NRS by:

- Duration of AD at Day 1 of current study (< 26 years, ≥26 years)
- Baseline body weight of current study ((<70 kg, ≥70-<100 kg, ≥100 kg)
- Baseline BMI of current study (<15, [15-25), [25-30), ≥30)
- Age (≥18-<40, ≥40-<65, ≥65)

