5.8.3. Analysis of Vital Signs

Summaries of vital sign variables will include:

- Descriptive statistics of vital sign variable and change from baseline by visit
- The number (n) and percentage (%) of patients with treatment-emergent PCSV, depending on data
- Shift tables based on baseline normal/abnormal and other tabular and graphical methods may be used to present the results for parameters of interest

Listings will be provided with flags indicating the treatment-emergent PCSVs, depending on data.

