- g. Patients will be trained on using the IVRS/IWRS at the baseline visit, and will call into the system weekly to report the overall intensity of their pruritus over the previous week, and to record compliance with self-injection of study drug.
- h. Patients will be provided with a pregnancy test kit to take home for monthly testing in between clinic visits, or may choose to have the testing done at the study site.
- i. An acceptable window for performing ophthalmology exams is within +/- 7 days of the visit date. This does not apply to the ophthalmology exam conducted at the baseline visit.

Table 6: Schedule of Events – Visits 19 (Week 60) through 24 (Week 100)

Study Procedures	Treatment Period						
	Visit (V)	V 19	V 20	V 21	V 22	V 23	V 24
	Week (Wk)	Wk 60	Wk 68	Wk 76	Wk 84	Wk 92	Wk 100
	Day (D)	D 421	D 477	D 533	D 589	D 645	D 701
Visit Window (d)	+/-3d	+/-3d	+/-3d	+/-3d	+/-3d	+/-3d	+/-3d
Treatment:							
Administer study drug ^a	X						
Patient dosing diary ^b	X	X	X	X	X	X	X
Study drug dispensation/account. ^c	X	X	X	X	X	X	X
Con meds/procedures	X		X			X	
Efficacy: ^d							
Patient Assessment of Pruritus Intensity via IVRS/IWRS (weekly) ^g	X						X
IGA, EASI	X						X
POEM, DLQI, EQ-5D ^e							X
Safety: ^d							
Weight	X		X				X
Vital signs	X		X	X	X	X	X
Ophthalmology exam ⁱ (select sites and patients)	X		X			X	
Adverse events ^f	X	X	X	X	X	X	X

Study Procedures	Treatment Period						
	Visit (V)	V 19	V 20	V 21	V 22	V 23	V 24
	Week (Wk)	Wk 60	Wk 68	Wk 76	Wk 84	Wk 92	Wk 100
	Day (D)	D 421	D 477	D 533	D 589	D 645	D 701
Visit Window (d)	+/-3d	+/-3d	+/-3d	+/-3d	+/-3d	+/-3d	+/-3d
Laboratory Testing: ^d							
Hematology, Chemistry							X
Pregnancy test, WOCBP only	Urine ^h , monthly throughout the study treatment						
Drug Concentration and Antibody Testing: ^d							
Drug Concentration sample							X
ADA sample							X

- a. Study drug will be administered weekly, either in the clinic or outside the clinic (self-administration or administration by a care provider).
- b. If needed, counsel patient on proper dosing diary completion/reporting of each dose of study drug that is administered outside of the clinic.
- c. Study drug will be dispensed to the patient for each dose that will be administered off-site between the current clinic visit and the next clinic visit. Patients will be instructed to return all study drug vials at each clinic visit.

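### SAP 6.4 places End of Study values of early stoppers in treatment-week rows, against SAP 5.7, and labels the on-treatment Week 260 visit End of study

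*SAP*

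**What the plan says.** SAP 6.4 divides by-visit data into two sets.

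- **All remaining data** (all other countries, plus data up to Amendment 6 from France, Germany, Poland, Japan and Finland). Scheduled visits keep their nominal label. For the others, analysis visit "windows will be used to map the unscheduled visits, early termination, end of treatment/ end of study visits, based on the study day". The opening of 6.4 gives the intent: the windows are exhaustive so that values from unscheduled visits, "early termination (ET) visit and end of treatment (EOT)/end of study (EOS) have the potential to be summarized". The order for choosing a record within a visit has as its second step: "Early termination (ET) or end of study (EOS), whichever comes first if scheduled visit not available".
- **Amendment 7/8 data from those five countries.** Scheduled visits are mapped by study day, but data from the "extension end of study visit or end of study visit under protocol amendment 7 or 8 will be summarized using the nominal visit". The last row of this table is labelled End of study, with target day 1821 and window 1794 or later. There is no Week 260 row.

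SAP 5.7, on efficacy, says: "Data collected under end of study visit (i.e. off-treatment measurement at the end of 12-week or 16-week safety follow up period) will be summarized separately". On-treatment data are what they are kept apart from. SAP 5.8.3, on vital signs, asks for "Descriptive statistics of vital sign variable and change from baseline by visit" and has no equivalent separation.

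Stopping before Week 148 was part of the design. SAP 2.3 Table 2 gives the treatment period under Amendments 4, 6 and 7 (global) as "148 weeks or until commercially available". Protocol 6.2.8 also asks patients who withdraw to attend EOS 12 weeks after their last dose.

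**The concern.** In the larger data set, 6.4 sends EOS records into week rows and 5.7 takes them out. Both rules name EOS, and neither yields to the other. Section 6.4 also treats the same visit in two ways, nominal in one set and day-mapped in the other, without giving a reason.

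IGA 0-1 and EASI-75 at each visit are the key secondary efficacy endpoints, and each proportion uses the patients with a value at that visit as its denominator. An EOS record therefore changes both numerator and denominator, and two programmers who each follow the SAP can produce different tables. For vital signs, nothing stops a value taken 12 or 16 weeks after the last dose from appearing under a treatment-week heading.

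The row label is a separate error. The five-year on-treatment visit would be reported as End of study, the same name the true EOS visit carries in that data set.

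**Working it through.** **Inputs**

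- Study day = 7 × week + 1 (target days in SAP 6.4).
- EOS = last dose + 84 days (12 weeks) or + 112 days (16 weeks), from SAP 2.3 Table 2. The V31 column of SAP 10.2 Table 7 allows either day 1121 or last dose + 84 days, so an early stopper's EOS is also V31.
- Windows for all remaining data (SAP 6.4): Week 60 [394, 449], Week 100 [674, 729], Week 124 [842, 897], Week 148 [1010, 1093], EOS from 1094. For the UK, EOS starts at 730.
- Post-baseline IGA/EASI weeks in the Amendment 7 schedule (SAP 10.2 Tables 4 to 7): 4, 16, 48, 60, 100, 124 and EOS. Vital signs are also taken at EOS.

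**1. The plan's own End of study days**

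- First table: 1037 + 112 = 1149, and for the UK 701 + 84 = 785. Both are true follow-up days.
- Amendment 7/8 table: 7 × 260 + 1 = 1821. Protocol 6.2.5 and SAP 10.2 Table 14 define day 1821 as Visit 44, Week 260, End of Treatment, with study drug given.
- (1765 + 1821)/2 = 1793, so a window starting at 1794 is the Week 260 window.
- EOS after a dose on day 1821 is 1821 + 84 = 1905, or 1875 to 1935 with the ±30-day visit window.
- Visit 44 (days 1818 to 1824) always falls in the row labelled End of study.

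**2. Where an early stopper's EOS lands**

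| Last dose | Day | EOS, 12 weeks | EOS, 16 weeks | Row assigned |
|---|---|---|---|---|
| Week 48 | 337 | 421 | 449 | Week 60 |
| Week 88 | 617 | 701 | 729 | Week 100 |
| Week 112 (non-UK) | 785 | 869 | 897 | Week 124 |

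The widest treatment window, [1010, 1093], spans 84 days, so two visits in one window are at most 83 days apart. EOS therefore never shares a window with the last dose. It fills its row unless a scheduled visit or an earlier ET visit falls in the same window.

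**3. How far this extends**

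- Non-UK: 1093 − 84 = 1009 (Week 144); 1093 − 112 = 981 (Week 140).
- UK: 729 − 84 = 645 (Week 92); 729 − 112 = 617 (Week 88).
- Counting weekly last doses from Week 0, EOS lands in a treatment row for 145 of 149 (12-week) or 141 of 149 (16-week) possible weeks outside the UK, and for 93 or 89 of 101 in the UK.
- Counting only the Amendment 7 IGA/EASI weeks, non-UK with 12-week follow-up: 4 (Week 16) + 4 (Week 48) + 8 (Week 60) + 8 (Week 100) + 8 (Week 124) = 32 of 149. Week 4 cannot be reached, because the earliest EOS is day 85.

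These are counts of possible stopping weeks, not of patients.

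**4. Reach of the label error at the second step cut-off**

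A visit on day 1794 by 01-Dec-2018 needs a first dose no later than 1793 days before, 3 January 2014. Day 1821 needs one 1820 days before, 7 December 2013.

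**The case against.** The best defence is that 5.7 is the specific efficacy rule and 6.4 a general convention. Section 6.4 says only that EOS values may be summarized, and its selection order is introduced as general. On this reading 6.4 assigns a label and 5.7 decides which table the record enters. A careful programmer might do that, but 6.4 also names EOS visits and directs them into the windows, so the SAP does not require it.

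Section 5.7 also uses all observed values after withdrawal from treatment, so an off-treatment value in a week cell is not an error in itself. That stands for ET and unscheduled values. The EOS sentence in the same section is narrower and removes EOS.

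For vital signs, SAP 5.8 counts safety observations through EOS and 6.4 counts days from first injection. So no rule is broken there. What remains is that follow-up values are pooled under week labels in one data set and kept nominal in the other.

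The three worked cases were chosen to hit scheduled IGA/EASI weeks, and only 32 of 149 stopping weeks do so under 12-week follow-up. That is fair. But Amendment 6 removed IGA/EASI from many other weeks, so later EOS values mapped there would join cells that have few scheduled values.

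Finally, off study treatment is not the same as off dupilumab. The documents do not say whether patients who stopped because the product became available used it before EOS.

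**Conclusion.** Both parts hold.

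For IGA and EASI in the all-remaining-data set, 6.4 and 5.7 give incompatible instructions for EOS records, and the SAP sets no precedence. Outside the UK the conflict covers every last dose up to Week 144 or Week 140, depending on follow-up length; in the UK, up to Week 92 or Week 88. This assumes EOS takes place on its due day; a late visit moves the row. Weekly pruritus NRS is not involved, because it has its own windows and its own separation rule. Amendment 7/8 data are not involved either, because EOS stays nominal there.

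The End of study label on day 1821 is wrong. The cut-points are right and few patients are likely to reach that row by the second step cut-off, so it matters mainly if the table is reused later.

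The documents give no last-dose dates, so neither the number of patients nor the shift in any proportion can be computed. No hypothesis is tested, and the TEAE primary endpoint does not use these windows. The point should be fixed because it makes key secondary tables depend on the programmer's reading, but it does not threaten the main safety conclusions.

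**What to change.** In SAP 6.4:

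1. Remove EOS visits from the study-day mapping for all remaining data and from step 2 of the record selection order. Summarize EOS efficacy and vital signs only under the nominal EOS visit, as 5.7 requires for efficacy and as 6.4 already does for Amendment 7/8 data.
2. Rename the last row of the Amendment 7/8 table Week 260 (EOT), with target day 1821 and lower limit 1794. Keep EOS nominal.
3. State that the all-observed rule of 5.7 still applies to ET and other post-withdrawal efficacy values.

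As a separate matter, reconcile the mapping of unscheduled laboratory and vital-sign values with Protocol 9.6, which keeps such values in listings and out of summaries.

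The cost is SAP wording and window programming. No new data are needed. Some sparse week cells will become smaller or empty.

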7. INTERIM ANALYSIS

This is an open-label extension study. No formal interim analyses will be planned for this study.

A first step analysis was performed to support the submission of market application for dupilumab in AD indication in third quarter of year 2016. All data prior to the cutoff date (11Apr2016) were included in this analysis. The process to derive the data cut-off for the first step analysis is outlined in [Appendix 10.7](#).

A second step analysis will be performed in first quarter of year 2019 in order to have long term data of dupilumab in AD indication. All data prior to the cutoff date (around 01Dec2018) for patients in Poland, Finland, Russia, New Zealand, Singapore and all data for patients from remaining countries will be included in this analysis. Patients from remaining countries will either complete or early withdrawn from the study at time of database lock. The process to derive the data cut-off for the second step analysis is outlined in [Appendix 10.8](#).

Future analyses will be performed to support the subsequent regulatory filings. The details and data cutoff date will be specified in future SAP addendum.

